2.1. Primary Objective

- To evaluate if treatment with RVX000222 as compared to placebo increases time to the first occurrence of narrowly defined MACE. Narrowly defined MACE is defined as a single composite endpoint of CV death or Non-fatal MI or Stroke.

2.2. Secondary Objectives

- To evaluate if treatment with RVX000222 increases time to the first occurrence of broadly defined MACE in comparison to placebo

Broadly defined MACE is the occurrence of any of the following events:

- CV death
- Non-fatal MI
- Hospitalization for CVD events including:
 - Unstable angina AND evidence of new or presumed new progressive obstructive coronary disease, OR
 - Emergency revascularization procedures at any time and urgent revascularization procedures ≥ 30 days after the index events prior to randomization
- Stroke
- To evaluate if treatment with RVX000222 increases time to the first occurrence of fatal or non-fatal MI, or fatal or non-fatal stroke.
- To evaluate treatment group difference in all-cause mortality
- To evaluate changes in lipoprotein concentrations including apoA-I, apolipoprotein B (apoB), LDL-C, HDL-C, and triglyceride (TG) over time within and between treatment groups
- To evaluate changes in DM variables including glycated hemoglobin (HbA1c), fasting glucose, and fasting insulin over time within and between treatment groups
- To evaluate changes in ALP over time within and between treatment groups including isoforms for whole population and quartiles of ALP baseline concentration
- Assess changes in kidney function in population with baseline estimated glomerular filtration rate < 60 mL/min/1.7m²
- To evaluate the safety and tolerability of RVX000222

2.3. Exploratory Objectives

- To evaluate changes in inflammation variables including, but not limited to, high-sensitivity C-reactive protein (hsCRP), fibrinogen, and inflammatory cytokines within and between treatment groups
- To evaluate transcription (messenger RNA [mRNA]) change in whole blood from baseline to 6 weeks of treatment
- To evaluate Health Related Quality of Life (HRQOL) as measured using the EQ-5D-5L
- To evaluate cognition changes in subject ≥ 70 years as measured using the MoCA scale

3. Investigational Plan

The sub-sections below re-iterate salient features of the investigational plan from the protocol as necessary context prior to the description of general statistical considerations, definitions of analysis populations and the proposed statistical approaches for the analyses of efficacy and safety data.

3.1. Overall Study Design and Plan

This is a double-blind, placebo-controlled, 2 arm parallel-group (allocation ratio 1:1), study of RVX000222 at a dose of 100 mg b.i.d. (total daily dose of 200 mg) or matching placebo in combination with high potency statin therapy administered to T2DM subjects with history of recent CVD event and HDL-C level < 40 mg/dL males or <45 mg/dL females. The high potency statin therapy shall consist of daily dose of either atorvastatin 20-80 mg or rosuvastatin 10-40 mg [20 mg atorvastatin or 10 mg rosuvastatin is only acceptable in circumstances such as advanced age, low body mass, previous intolerance to higher doses or specific drug-drug interactions (e.g. anti-retrovirals).

After an initial screening period of 1 to 2 weeks during which subjects will be treated with standard of care high potency statin therapy, subjects will be randomized to either RVX000222 100 mg b.i.d. or matching placebo with continued statin treatment. This combination treatment period will continue until 250 narrowly defined MACE events have occurred in the study and all surviving subjects have been followed for at least 24 weeks from randomization. Blinded treatment with RVX000222 or matching placebo will then be discontinued. Subjects will remain on standard of care high potency statin therapy for 4 more weeks until the Follow-Up Visit.

The study is an event-based trial and will continue until 250 narrowly defined MACE events have occurred. The study will be monitored by a Data Safety Monitoring Board (DSMB). MACE will be adjudicated by an independent MACE Adjudication Committee (EAC) in an ongoing manner. Study data as indicated on the Schedule of Events (See the study protocol) will be collected at each study visit and recorded in the appropriate sections of the eCRF.

3.2. Study Endpoints

3.2.1. Primary Endpoint

The primary endpoint will be time from randomization to the first occurrence of adjudication confirmed MACE narrowly defined as a single composite endpoint of CV Death or Non-fatal MI or Stroke.

3.2.2. Key Secondary Endpoints

The key secondary endpoints will be:

1. Time from randomization to the first occurrence of adjudication-confirmed MACE broadly defined between treatment groups.
Broadly defined MACE is the occurrence of any of the following events:
 - CV death Non-fatal MI
 - Hospitalization for CVD events which include:
 - Unstable angina AND evidence of new or presumed new progressive obstructive coronary disease, OR

- Emergency revascularization procedures at any time and urgent revascularization procedures ≥ 30 days after the index events prior to randomization
 - Stroke
- 2. Total incidence of Narrow MACE
- 3. Time from randomization to CV Death or Non-fatal MI
- 4. Time from randomization to coronary heart disease (CHD) death or Non-fatal MI
- 5. Time from randomization to Non-fatal MI
- 6. Time from randomization to CV Death
- 7. Time from randomization to Stroke
- 8. All-cause mortality
- 9. Incidence of hospitalization for congestive heart failure (CHF)

3.2.2.1. Other Secondary Endpoints

- The percent change in apoA-I, apoB, LDL-C, HDL-C, and TG over time within and between treatment groups
- The change from baseline in HbA1c, fasting glucose, and fasting insulin within and between treatment groups
- Changes in ALP within and between treatment groups for all subjects and according to quartiles of ALP baseline concentration
- Changes from baseline in kidney function in subgroup population with estimated glomerular filtration rate < 60 mL/min/1.7m² within and between treatment groups

3.2.3. Exploratory Endpoints

- The percent change in hsCRP, fibrinogen, and inflammatory cytokines within and between treatment groups
- Change in MoCA score in all and those with baseline MoCA < 26 within and between treatment groups
- Transcription/mRNA change in whole blood from baseline to 6 weeks treatment within and between treatment groups
- Change in Health Related Quality of Life (HRQOL) as measured using the EQ-5D-5L

3.2.4. Safety Endpoints

- Safety assessments will include incidence of adverse events (AEs), serious adverse events (SAEs), vital sign measurements, clinical laboratory evaluations, and physical examination findings.

3.3. Study Drugs

RVX000222 is available as a capsule formulation with standard excipients and established stability. Placebo for RVX000222 is available as a capsule formulation free of RVX000222 API. It is comprised of standard excipients and has established stability.

RVX000222 (200 mg BID) will be taken orally with food in the morning and evening, approximately 10-12 hours apart. In certain situations the dose may be decreased to 100 mg daily (50 mg b.i.d.; refer to the protocol). Per protocol, if a dose is missed, subject should take missed dose at the time it is remembered, unless it is within four hours of the next scheduled dose. If within four hours of the next schedule dose,

the missed dose should be skipped. Subjects will take their first dose of study drug while in clinic during Visit 2.

3.4. Study Drug Interruption/Discontinuation

Treatment may be interrupted or discontinued at the discretion of the Investigator and Sponsor, based on AEs, other clinical laboratory data, vital signs measurements, and/or electrocardiogram (ECG) findings.

Subjects discontinuing study drug will continue participation in the study and will complete all remaining study visits. Discontinuation of assigned study drug (RVX000222 or placebo) or high intensity statin therapy should not result in study discontinuation.

3.5. Concomitant Statin Therapy

Protocol defined concomitant treatment in this study is 20-80 mg atorvastatin or 10-40 mg rosuvastatin once daily orally. 20 mg atorvastatin or 10 mg rosuvastatin are acceptable in circumstances such as advanced age, low body mass, or specific drug-drug interactions (e.g. anti-retrovirals).

Subjects will receive concomitant statin therapy as stated in section 6.6 in the protocol.

The statin dose shall be administered daily in the morning at the same time as the RVX000222 dose (or placebo) and within 30 minutes of completion of a meal. Per protocol, if a dose is missed, subject should take missed dose at the time it is remembered, unless it is within four hours of the next scheduled dose. If within four hours of the next schedule dose, missed dose should be skipped.

3.6. Background Therapy

The subject's other background therapy for dyslipidemia and any coexisting conditions such as CAD, hypertension and diabetes should, in the investigator's opinion, adhere to acceptable standards of care and preferably remain unaltered during the treatment period unless clinically indicated.

3.7. Study Visits

After randomization to RVX000222 or placebo, visits will occur every 2 weeks until Week 12. From Week 12 to Week 28, visits will occur every 4 weeks. From Week 28 until the Last Visit on Treatment, visits will occur approximately every 12 weeks. Four weeks after the Last Visit on Treatment, subjects will return for a final Follow-Up Visit. The Schedule of Events can be found in the study protocol. Study treatment will be terminated in all currently participating subjects when it is estimated that 250 subjects have experienced a narrowly defined MACE event. At that time, all subjects actively treated will conduct their Last Visit on Treatment as soon after as possible while ensuring at least 6 months of study therapy and then return 4 weeks after last day of treatment for the Follow-Up Visit. Procedures are defined in the Schedule of Events.

3.8. Dose Adjustment/Modifications

Additional safety lab monitoring will occur and study drug may be interrupted, reduced, and/or permanently discontinued if the subject meets following criteria. If ALT increases $>3 \times \text{ULN}$ or serum bilirubin increases $>2 \times \text{ULN}$, subjects will be notified and repeat chemistries obtained as soon as possible.

1. If ALT increase of 3-5xULN is confirmed on repeat measurement (within 3-4 days), subjects will be monitored every 3-4 days until the ALT is <1.5xULN.
2. If ALT increase of >5xULN, study drug will be suspended. If confirmed on repeat measurement (within 3-4 days), study drug will be permanently discontinued and subjects will be monitored every 3-4 days until the ALT is <1.5xULN.
3. If serum bilirubin increase of >2xULN is confirmed on repeat measurement (within 3-4 days), then study drug will be permanently discontinued and subjects will be monitored every 3-4 days until levels are within normal range.

Subjects who have an ALT increase of $\geq 3xULN$ will be monitored by liver safety panels [ALT (SGPT), AST (SGOT), GGT, ALP, bilirubin (direct and total)] and have archival serum samples drawn every 3-4 days until ALT is <1.5xULN.

Subjects who have an ALT increase of >5xULN or who have a serum bilirubin increase of >2xULN will be monitored by extended liver safety panels [ALT (SGPT), AST (SGOT), GGT, ALP, bilirubin (direct and total), as well as osteopontin and PT INR] and have archival serum samples drawn every 3-4 days until ALT is <1.5xULN and serum bilirubin levels are in within the normal range.

Per protocol, subjects should continue to follow the protocol-defined assessments according to the Schedule of Events in the protocol until study completion.

If the ALT elevation has cause (e.g. trauma, infection-inflammation, surgery, acetaminophen, clavulanic acid, diclofenac) treatment may be restarted at 50 mg b.i.d. once ALT returns to 1.5 xULN and subjects should continue with all scheduled study visits according to the Schedule of Events and will have additional liver safety panel tests drawn according to the original study schedule:

- Weeks 0-12 after study drug is reinitiated: liver safety panel every 2 weeks (Weeks 0, 2, 4, 6, 8, 10, 12 after re-initiation)
- Weeks 12-28 after study drug is reinitiated: liver safety panel every 4 weeks (Weeks 16, 20, 24 after re-initiation)
- Weeks 28 after investigational drug is reinitiated to end of treatment: liver safety panel approximately every 12 weeks (Weeks 40, 52, 64, 76, 88, 100)

Re-initiation of study drug will be discussed with and approved by the study medical monitor prior to dosing.

4. General Statistical Considerations

4.1. Reporting Conventions and Dates Handling

Derived analysis data sets will be produced from the electronic case report form (eCRF) data, central laboratory data and the electronic adjudication data (EAS) to assist with analysis and summary of both efficacy and safety endpoints. Derived data sets will identify observations selected according to the study window convention described in [section 4.5](#) and values that will be summarized.

The number and percentage of subjects will be used to summarize categorical variables. When count data are presented and the count is zero, the percentage will be suppressed. Unless otherwise specified, the denominator for percentages will be the number of subjects in a given treatment group within the analysis set of interest. Descriptive statistics (number of subjects with non-missing values, mean, standard deviation, minimum, 25th percentile, median, 75th percentile, and maximum) will be used to summarize continuous variables unless otherwise noted.

In summary tables for categorical data, all categories will be presented if they are specified on the eCRF (eg, discontinuation reason), or if categories are ordered intervals (eg, age groups), regardless of whether or not a subject is found in a given category. For other categorical data (eg, AEs and medications), only categories with at least 1 subject will be presented. A row denoted “Missing” will be included in count tabulations where specified on the shells to account for dropouts and missing values. When no data are available for a table or listing, an empty page with the title will be produced with suitable text (eg, “There are no observations for this table/listing.”).

Means and percentiles will be presented to 1 more decimal place than the recorded data. Standard deviations and standard errors will be presented to 2 more decimal places than the recorded data. Minimum and maximum values will be presented using the same number of decimal places as the recorded data. Percentages will be presented to 1 decimal place. Hazard ratios will be presented with 3 decimal places. Confidence intervals (CIs) will be presented using the same number of decimal places as the parameter estimate (eg, LS mean or hazard ratio).

Subjects are uniquely identified by a concatenation of study center number and subject number. All data available from the eCRFs along with some derived variables will be listed. For relevant dates, the actual day relative to start of double-blind treatment will also be listed. Dates will be presented in the format of “DDMMYYYY”.

4.2. Sample Size Justification:

The study design will provide approximately 80% power to declare superiority of RVX000222 arm over Placebo with a hazard ratio of 0.7, a true hazard ratio of 1.0 and at an overall 2-sided 5% significance level.

To calculate the sample size (number of subjects), the following additional information was assumed:

- Total number of narrowly defined MACE events needed: 250
- 10.5% event rate in the placebo arm at 18 months
- 30% relative risk reduction (7.47% event rate at 18 months in the RVX000222 arm)
- Accrual period of 1.7 years (20 months) and a total study duration (including follow-up) of 2.75 years (143 weeks)
- A cumulative drop-out rate of 10% per arm by the end of the study (5% drop out rate per arm by year one)

With the above design and assumptions, a sample size of approximately 2400 randomized subjects enrolled uniformly over 1.7 years with total study duration of 143 weeks and subjects followed until failure, drop out or end of study is estimated to provide the 250 events needed.

The power and sample size for this study was calculated using East 6.2.

4.3. Randomization, Stratification, and Blinding

4.3.1. Randomization

All qualified subjects will be randomly assigned in a ratio of 1:1 to one of the following two treatment arms: RVX000222 200 mg daily or matching placebo. Randomization will be stratified by country and high intensity statin therapy within the country (i.e. atorvastatin or rosuvastatin). Further, randomization will be dynamically restricted to assure that statin therapy imbalance is no greater than 60:40 (or 40:60) within each country. Study participants will only be directed (per informed consent) to switch their statin therapy to rosuvastatin or atorvastatin once randomization limits are reached on either statin to minimize enrollment impact.

A randomization schedule will be generated for the IWRS and will be implemented by the IWRS prior to dosing at Visit 2. The IWRS will allocate the study drug via the prepared randomization scheme and will provide the randomization number and appropriate drug package numbers. The IWRS process to achieve an approximate even split of study participants across the statin levels per country will be described in greater detail in the IWRS specifications. The subject should always be provided study drug with the number allocated by the IWRS.

4.3.2. RVX000222 Treatment Blinding

The blinding is ensured by using double-blind RVX000222 study drug. Placebo capsules will be equally matched in size, shape, and color to RVX000222 and will be packaged in the same manner. The study drug packaging will be labeled with unique identification numbers allocated from the IWRS.

Subjects, investigative staff, persons performing the assessments, and data analysts will remain blind to the identity of the treatment from the time of randomization. No member of the CSC, the study team at Resverlogix, personnel at study centers, or any clinical research organization (CRO) handling data will have access to the randomization scheme during the course of the study, with the exception of the study personnel generating the randomization scheme, the personnel preparing DSMB data for review, the DSMB itself, the personnel providing IWRS and carrying out the packaging and labelling of investigational products. Unblinding will occur in the case of subject emergencies when knowledge of the treatment assignment would affect subject care and at the conclusion of the study.

4.4. Analysis Set

The following 3 analysis sets will be used.

4.4.1. Full Analysis Set (FAS)

The FAS will include all randomized subjects who receive any amount of study therapy and have at least one measurement of the assessment of interest. All efficacy analyses will be conducted for the FAS. Subjects will be analyzed based on randomized treatment group. Subjects experienced study drug dose adjustment will be included in the FAS and their data will be analyzed according to the randomized treatment group.

4.4.2. Per-protocol Set (PPS)

The PPS will consist of all FAS subjects who fulfill all inclusion/exclusion criteria, and have no major protocol violations. The major protocol violation criteria will be finalized by the Clinical Science and Biostatistics teams as part of the masked data reviews prior to the interim and final database locks. Likewise, whenever possible, subjects belonging to the PPS will be determined prior to the interim and final database locks. Subjects will be analyzed based on the treatments received most often. The list of major protocol violations is provided in [section 5.2](#) of this statistical analysis plan.

4.4.3. Safety Set (SS)

The SS will include all subjects who took at least one dose of double-blind study therapy. In safety summaries, subjects will be analyzed according to the actual treatment received. All safety analyses will use the SS.

4.5. Definition of Time Points, Study Dates, Visit Windows, and Duration

Study Day 1 is defined as the day of randomization when subjects will receive the first dose. Other study days are defined relative to Study Day 1, e.g. the day prior to Study Day 1 is Day -1 and the day after Study Day 1 is Day 2. Study days will not be computed for subjects who are not randomized.

All scheduled study visits will be defined relative to Study Day 1. For example, the appropriate day for the scheduled Week 2 visit should be: Day 1 + 14 = Day 15. A windowing convention which will be used to determine the analysis value for a given study visit will be applicable for all by-visit summaries and analyses. The study visit window can be found in the “Schedule of Events” in the study protocol and also presented in the following table below:

Table 1: Visit Windows for Efficacy and Safety Variables

Study Week	Scheduled Day	Study Day Range
0	Baseline (Day 1)	<=1
2	15	12 18
4	29	26 32
6	43	40 46
8	57	54 60
10	71	68 74
12	85	82 88
16	113	110 116
20	141	138 144
24	169	166 172
28	197	194 200
40*	281	274 288
52	365	358 372
64	449	442 456
76	533	526 540
88	617	610 624
100	701	694 708
112	785	778 792

*Visits to occur with +/- 7-day window past week 40 every 12 weeks

Study treatment will be terminated in all currently participating subjects when the 250th event occurs and all surviving patients have been followed for at least 24 weeks from randomization. At that time all subjects actively treated will conduct their Last Visit on Treatment. Follow up visit is to be scheduled 4 weeks after last visit on treatment. Last visit on treatment and follow up are subject to +/-7 day window.

The baseline value for a variable is defined as the last observation collected on or before Study Day 1/first dose date & time; it cannot be substituted for any post-baseline value. Unscheduled visits or Study visits that are outside the protocol defined windows will be mapped to the closest study visits. All safety data with incomplete dates will be forwarded to Data Management for query.

One or more results for a particular variable may be obtained in the same visit window due to unscheduled or repeated measurements. In such events, the result with the date closest to the expected visit date (scheduled day) will be used. In the event that 2 observations equidistant from the expected visit date are available, the later observation will be used.

If the CRF dates are needed for variable derivation or calculation and they are missing after querying the sites, the imputation rules below will be employed. However, no results or outcomes will be imputed.

- If the day is missing in the interim data cut, impute missing day as 15th of the month.
- If the month is missing, impute the month as July.
- Additionally, if both day and month are missing, impute to 15JUL.

- If month/year of the onset date is on or after the month/year of Study Day 1, the AE will be considered on-study;
- If month/year of the onset date is equal to the month/year of Study Day 1, and the end date is present, the end date will be used to determine when the AE resolved. If the end date is on or after Study Day 1, the AE will be considered on-study; otherwise, if the AE stopped before Study Day 1, then it will not be on-study; If month/year of the onset date is equal to the month/year of Day 1, and the end date is a partial date, the AE will be considered on-study.

In addition, durations (e.g. treatment duration) will be measured in weeks and will be calculated as:
(End Date – Start Date + 1)/7.

- Intervals that are presented in weeks will be transformed from days to weeks by using (without truncation) the following conversion formula:
WEEKS = DAYS /7.
- Intervals that are presented in months will be transformed from days to months by using (without truncation) the following conversion formula:
MONTHS = DAYS /30.4375.

5. Subject Disposition

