5.2 Inclusion Criteria

Subjects who meet the following criteria may be enrolled:

1. Male and female subjects age 18 and over with documented diagnosed T2DM and a CAD event of either unstable angina or myocardial infarction, not less than 7 days and no more than 90 days prior to Visit 1. In order to have sufficient number of clinical events, the number of subjects with unstable angina will be limited to 25% of the total number of subjects.

- Unstable angina: for a qualifying unstable angina event, each of components (a), (b), and (c) must be satisfied:
 - a. Characteristic ischemic pain or discomfort in chest or associated referral areas, occurring at rest or with minimal exertion
 - b. ECG changes consistent with acute myocardial ischemia based upon at least one of the following:
 - i. new or presumed new ST elevation
 - ii. new or presumed new ST depression
 - iii. new or presumed new T-wave inversion
 - c. Objective evidence of obstructive coronary artery disease based upon at least one of the following:
 - i. new or presumed new evidence of myocardial ischemia or infarction by perfusion imaging
 - ii. new or presumed new regional wall motion abnormality
 - iii. current evidence of at least one epicardial coronary artery stenosis $\geq 70\%$ by coronary angiography
 - iv. need for coronary revascularization for the index ACS event, including percutaneous coronary intervention (PCI) with or without coronary stenting
 - Previous MI 7-90 days before screening, treated with or without a percutaneous coronary intervention (PCI). For a qualifying event of MI, **two of the following three criteria must be satisfied**:
 - a. Characteristic ischemic chest pain or pain in associated referral areas
 - b. Dynamic elevation of troponin T or I or CKMB, if troponin T or I is unavailable at the local lab (at least above the upper limit of normal for the laboratory)
 - c. Development of new Q-waves in at least two adjacent ECG leads, or development of a new dominant R wave in V1
2. Documented diagnosis of T2DM (one or more of the following criteria must be met):
 - Documented history of T2DM
 - History of taking diabetes medication
 - HbA1c $\geq 6.5\%$ at Visit 1
 3. For males HDL-C of <40 mg/dL (1.04 mmol/L) and for females HDL-C of <45 mg/dL (1.17 mmol/L) at Visit 1.
 4. In the opinion of the Investigator, subjects currently not on high intensity statin therapy will be able to start rosuvastatin according to the protocol at Visit 1.

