7.2.1 Screening/ Study Visit 1 (Week -2 to -1)

Before any study-specific procedures are performed, the subject must receive an explanation of all study procedures, have an opportunity to ask questions, and must sign and date an Institutional Ethics Committee (IEC) approved written informed consent form.

The following will be conducted at Screening:

- Assess inclusion/exclusion criteria
- Document in the subject's medical records the participation in this clinical trial, that informed consent has been obtained, and that a copy of the signed informed consent form has been given to the subject.
- Prepare subjects for the first treatment period participation by informing them of study restrictions and study procedures
- Record demographics
- Measure height and weight
- Review and record complete medical history (including CV history)
- Record prior and concomitant medications (including all CV medications), including detailed information related to the dose, starting and end dates for all medications. Prior medications taken during the 30 day period before Visit 1 will be collected
- Measure vital signs
- Perform a physical examination
- Perform a standard 12-lead ECG
- Collect clinical laboratory samples: fasting lipid profile, hematology, HbA1c, chemistry, urinalysis, liver safety panel
- Perform serology for hepatitis A, B, and C viruses
- Perform urine pregnancy test (female subjects of childbearing potential only)
- Subjects will continue or begin high intensity statin therapy as described in Section 6.6.

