7.2.2 Study Visit 2/Randomization (Week 0)

- Review inclusion and exclusion criteria
- Record any AEs
- Record concomitant medications
- If subject satisfies all inclusion and exclusion criteria, randomization may occur
- Measure vital signs
- Collect clinical laboratory test samples: liver safety panel
- Collect biomarker laboratory test samples in a selected subset of subjects: lipoproteins, fasting insulin, and inflammation panel
- Collect serum/plasma archive samples
- Collect blood samples for pharmacogenomic testing (DNA and RNA) if subject consent received
- Perform MOCA test for any subjects ≥ 70 years of age at randomization
- Administer EQ-5D-5L
- Dispense investigational drug
- Dispense high intensity statin

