7.2.8 Study Visit 11 (Week 24)

- Measure vital signs
- Collect clinical laboratory test samples: fasting lipid profile, hematology, HbA1c, chemistry, urinalysis, liver safety panel
- Collect biomarker laboratory test samples in a selected subset of subjects: lipoproteins, fasting insulin
- Administer EQ-5D-5L
- Record concomitant medications
- Monitor AEs
- Perform drug accountability; dispense investigational drug; dispense high intensity statin

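### Baseline LDL-C, HDL-C and triglycerides are screening values, so within-arm lipid changes can mix regression to the mean and statin effect with drug effect; between-arm contrasts are not biased

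*SAP*

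**What the plan says.** The baseline rule in SAP 4.5 is general: "The baseline value for a variable is defined as the last observation collected on or before Study Day 1/first dose date & time". SAP 3.2.2.1 lists as an other secondary endpoint "The percent change in apoA-I, apoB, LDL-C, HDL-C, and TG over time within and between treatment groups".

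The visit lists in the protocol fix which sample that rule selects:

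- Visit 1 (Protocol 7.2.1): "Collect clinical laboratory samples: fasting lipid profile, hematology, HbA1c, chemistry, urinalysis, liver safety panel".
- Visit 2, the day of randomization and first dose (Protocol 7.2.2): "Collect clinical laboratory test samples: liver safety panel" and "Collect biomarker laboratory test samples in a selected subset of subjects: lipoproteins, fasting insulin, and inflammation panel". The schedule footnotes define lipoproteins as apoA-I and apoB.
- Week 24 (Protocol 7.2.8): "Collect clinical laboratory test samples: fasting lipid profile, hematology, HbA1c, chemistry, urinalysis, liver safety panel".

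The schedules of events in both documents agree with these lists.

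Two other things happen at Visit 1. Eligibility on HDL-C is decided there: "For males HDL-C of <40 mg/dL (1.04 mmol/L) and for females HDL-C of <45 mg/dL (1.17 mmol/L) at Visit 1" (Protocol 5.2). Protocol 5.3 excludes subjects with triglycerides above 400 mg/dL at the same visit. Statin therapy is also settled there: "Subjects will continue or begin high intensity statin therapy as described in Section 6.6" (Protocol 7.2.1). The synopsis places the laboratory draw before the statin step.

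For analysis, SAP 8.4 plans descriptive change by arm at each visit, an ANCOVA with treatment, baseline and strata, and an MMRM. Neither document mentions a second pre-dose lipid profile or any caution about within-arm change.

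**The concern.** A baseline used to measure change should come from the same conditions as the follow-up values, apart from the study drug, and preferably should not be the measurement that selected the subject. For these three lipids neither holds in full.

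- **HDL-C.** Subjects enter because one reading was low. A later reading will on average be higher, with no treatment at all.
- **Triglycerides.** The upper limit acts the same way, upward, but only by removing the extreme tail, so the effect should be weak.
- **LDL-C.** There is no entry limit. Here the issue is statin effect: in anyone whose statin is started, intensified or switched at Visit 1, the baseline predates the change and Week 24 follows it.

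At stake is how the within-arm half of the endpoint is read. The sponsor's earlier reporting shows why this matters. Table 2 in Protocol 1.0 gives a p value against baseline for each arm. For hs-CRP both arms fell significantly (placebo -22.4%, p=0.0002; active -28.4%, p<0.0001), while the comparison between arms gave p=0.67. Within-arm significance said nothing there about the drug.

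**Working it through.** The plan gives no power, SD or expected change for any lipid endpoint, so there is no figure of its own to reproduce. The calculations below use assumed inputs, marked as such.

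**Step 1. Which sample is the baseline?**

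| Visit | LDL-C, HDL-C, triglycerides | apoA-I, apoB (subset) |
|---|---|---|
| Visit 1 (screening) | drawn | not drawn |
| Visit 2 (Week 0) | not drawn | drawn |
| Visit 11 (Week 24) | drawn | drawn |

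The last scheduled pre-dose value is therefore Visit 1 for the three lipids and Visit 2 for the apolipoproteins. An unscheduled lipid sample before first dose would replace the Visit 1 value under the rule, but none is planned.

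**Step 2. Regression to the mean in HDL-C.** From the documents: the male cut-off of 40 mg/dL. Assumed: unselected mean μ of 36 to 44 mg/dL, SD σ of 8 to 11 mg/dL, and test-retest correlation r of 0.7 to 0.9. With a = (40 − μ)/σ:

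- mean of the selected first readings: m = μ − σ·φ(a)/Φ(a)
- expected rise with no treatment: (1 − r)·(μ − m)

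Worked case, μ=40, σ=10, r=0.8: a=0 and φ/Φ=0.798, so m=40−7.98=32.02. The rise is 0.2×7.98=1.60 mg/dL, and 1.60/32.02=5.0%.

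| μ, σ | m | r=0.9 | r=0.8 | r=0.7 |
|---|---|---|---|---|
| 36, 8 | 31.93 | 0.41 (1.3%) | 0.81 (2.6%) | 1.22 (3.8%) |
| 40, 10 | 32.02 | 0.80 (2.5%) | 1.60 (5.0%) | 2.39 (7.5%) |
| 44, 11 | 32.53 | 1.15 (3.5%) | 2.29 (7.1%) | 3.44 (10.6%) |

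Cells are mg/dL, with percent of m in parentheses.

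**Step 3. The same on the scale of the Phase 2 table, which reports medians.** Paired readings were simulated with no treatment effect, keeping first readings between 15 and 40 mg/dL, and then split at random into two arms.

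| μ, σ, r | Mean % change | Median % change | Between-arm difference in mean % change (points) |
|---|---|---|---|
| 36, 8, 0.9 | 1.62 | 1.23 | 0.016 |
| 40, 10, 0.8 | 5.76 | 4.78 | −0.005 |
| 44, 11, 0.7 | 11.74 | 10.18 | −0.075 |

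For reference, the Phase 2 median HDL-C changes were 7.69% on active drug and 0 on placebo (Protocol 1.0, Table 2).

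**Step 4. Statin effect on LDL-C.** Within-arm shift = −(share changing statin) × (fall in those subjects). Both inputs are assumed.

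| Share changing | 10% fall | 25% fall | 45% fall |
|---|---|---|---|
| 10% | −1.0% | −2.5% | −4.5% |
| 30% | −3.0% | −7.5% | −13.5% |
| 50% | −5.0% | −12.5% | −22.5% |

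Statin changes at Visit 1 precede randomization, so this shift is expected equally in both arms.

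**The case against.** The strongest reply is that little inference rests on within-arm change.

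- **No within-arm test is named.** The SAP specifies no paired or signed-rank test. The word *within* sits in the endpoint label, and the model is a comparison between arms. This largely stands. However, the LS-mean sentence in SAP 8.4 can be read as giving confidence intervals and p-values for each arm as well as for the difference, and the endpoint itself names within-arm change. The text should settle which is meant.
- **The placebo arm is shown alongside.** A careful reader will compare the two. True, but the endpoint as worded does not require it.
- **Phase 2 evidence points to a small effect.** The two trials pooled in Table 2 enrolled statin-treated subjects with low HDL-C, and placebo HDL-C changed by a median of 0 (p=0.59). This is the best evidence in the documents and favours the low end of the range. It is not decisive: baseline sampling in those trials is not described, and placebo apoA-I rose 3.8% (p=0.0003).
- **The sizes are assumed, and only the male cut-off is modelled.** This stands in full.
- **Many subjects may have no statin change.** All are 7 to 90 days past an MI or unstable angina, and those already on protocol-defined therapy continue it. The share who change is not given.
- **These endpoints are supportive** and outside multiplicity control. This stands and limits the importance of the point.

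**Conclusion.** The point holds for within-arm percent change in LDL-C, HDL-C and triglycerides. The Visit 1 baseline follows from the documents without assumption. The size does not: an HDL-C rise of roughly 1% to 10% rests on assumed means, SDs and correlations, and the LDL-C shift (−1% to −22.5% in the grid) rests on an unknown share of subjects and an assumed fall. It would be too strong to say that HDL-C will rise and LDL-C will fall in both arms. The documents support only that such shifts can occur and could not be told apart from drug effect within an arm.

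A reader might also infer more than the documents bear out:

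- **That the lipid comparison between arms is biased.** It is not. Both mechanisms act before randomization or equally after it.
- **That the event analyses are affected.** The primary and key secondary analyses do not use lipid baselines.
- **That the LDL/HDL/TG median subgroups in SAP 8.2 are invalid.** A pre-randomization value is a legitimate subgroup variable whether or not it predates a statin change.
- **That the different apolipoprotein baseline breaks an analysis.** ApoA-I and apoB are measured in at most 600 subjects, and no paired or ratio analysis with LDL-C or HDL-C is planned.

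The change is worth making because it is nearly free, but it does not bear on the trial's main conclusions.

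**What to change.** Amend SAP 3.2.2.1 and 8.4 as follows.

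1. For LDL-C, HDL-C and triglycerides, make the LS mean difference between RVX000222 and placebo the only inferential result.
2. Report within-arm changes descriptively, without p-values. Add a table note that baseline is the Visit 1 sample, which was used for HDL-C and triglyceride eligibility and was drawn before any statin change at that visit.
3. Add statin status at Visit 1 (continued versus started or changed, counting a dose change as changed) to the ANCOVA and MMRM for these lipids. It is fixed before randomization. It can be derived from the prior-medication record, which holds doses and dates (Protocol 7.2.1), and from the IWRS record of statin transitions (Protocol 6.6). The existing strata capture country and statin type, not whether therapy changed.

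The covariate should improve the precision of the comparison between arms, by an amount not estimated here. It does not correct within-arm change, which is why items 1 and 2 are needed. The cost is SAP wording and one extra derived variable.

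A fasting lipid profile at Visit 2 is optional only. It would remove most of the regression to the mean but only part of the statin effect, since it follows just 1 to 2 weeks of the changed therapy. It also costs more than one added assay. Fasting tests at Visit 2 apply to a subset of up to 600, so about 2400 − 600 = 1800 subjects would face a new fast of 9 to 12 hours (Protocol 7.1.4). The fast would have to be fitted around a first dose taken in clinic with a meal (Protocol 6.5).
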